The CES-D is a 20-item survey assessing affective depressive symptomatology to screen for risk of depression³⁸. Scores range from 0-60, with a score of 16 commonly used as a clinically relevant cut-off ³⁹.

GAD-7

The GAD-7 is a seven item screening tool for anxiety that is widely used in primary care⁴⁰.

EQ-5D

Health-related quality of life is measured by the EQ-5D with each data collection visit⁴¹. The EQ-5D consists of 5 items assessing an individual's current health status (values from 0-2), yielding scores ranging from 0-10. Overall health status is also assessed with values from 0-100.

Compass 31

The Compass 31 is a 54 item, abbreviated quantitative measure of autonomic symptoms⁴².

The RPQ is a 16-item survey that assesses the severity of the most common post-concussion symptoms on a scale of 0 to 4. Items are compared to levels before the head injury and are reported as a 24 hour recall⁴³.

Physiological measures (HR/BP/HRV/BRS)

Blood Pressure (BP), Heart Rate (HR), Heart Rate Variability (HRV), and Baroreflex Sensitivity (BRS)

Continuous BP and HR are acquired from noninvasive finger arterial pressure measurements and ECG for a minimum of 10 minutes in subjects lying down quietly, supine. Systolic BP and beat to beat, RR, intervals (RRI) files generated via the data acquisition system (BIOPAC acquisition system and software, Santa Barbara, CA) at 1000 Hz are analyzed using Nevrokard BRS software (Nevrokard BRS, Medistar, Ljubljana, Slovenia) for measures of BRS, HRV and BPV as follows: Frequency Method. Power spectral densities of SBP and RRI oscillations are computed by 512 points Fast Fourier Transform (FFT) and integrated over specified frequency ranges (LF: 0.04-0.15 Hz; HF: 0.15-0.4 Hz). A Hanning window is applied and the squared-coherence modulus is computed if coherence is > 0.5 as reported. The square-root of the ratio of RRI's and SBP powers is computed to calculate LF, HF alpha indices, which reflect BRS. Power of RRI spectra in LF, HF range (LFRRI and HFRRI) are calculated in normalized units and the ratio of LFRRI/HFRRI is used as a measure of sympatho-vagal balance. Power of SBP spectra calculated as LFSAP is used as a measure of BPV. Sequence Method - BRS calculated by this method is based on quantification of sequences of at least three beats (n) in which SBP consecutively increases (UP sequence) or decreases (DOWN sequence), which are accompanied by changes in the same direction of the RRI of subsequent beats (n+1). The software scans the RRI and SBP records, identifies sequences, and calculates linear correlation between RRI and SBP for each sequence. If the correlation coefficient exceeds a pre-set critical value (0.85), the regression coefficient (slope) is calculated and accepted. The mean of all individual regression coefficients (slopes), a measure of sequence BRS, is then calculated for Sequence UP, DOWN and TOTAL. Time-Domain Analysis - Three time-domain parameters are used for hemodynamic variability. HRV is determined by computing the standard deviation of beat-to-beat interval (SDNN) and the root mean square of successive beat-to-beat differences in R-R interval duration (rMSSD).

a) HRV Data Processing and Interpretation

Heart rate is measured as beat-to-beat intervals (RRI) recorded by pulse-wave recording, and will be analyzed using custom software developed by Biopac. Data can be loaded and viewed, and a subset of the data can be selected to avoid artifacts during device placement or removal. Outlier identification is performed by determining all inter-beat intervals which demonstrate a 30% difference from the mean of the previous four samples. Such outliers are removed from the data set. HRV statistics that are generated include mean, variance, SDNN, RMSSD, pNN50, VLF, LF, HF, TP, LF/HF, sample

Version 1.0 10/06/2017

rpq

asymmetry, sample entropy, and coherence. All of the algorithms for computation of these parameters are derived from information or source code from the Physionet archive. Data are saved to Excel spreadsheets for further statistical analysis by study team members.

b) Blood Pressure (BP)

Blood pressure (BP) measurements will be taken with a finger cuff on two fingers of the left hand while lying down on an examination table.

Functional Measures:

Reaction Time

Reaction time testing will be measured by a drop-stick, clinical reaction time apparatus. It is constructed from a meter stick covered in the friction tape with gradations. The modified meter stick is fixed to a weighted rubber cylinder. The apparatus is placed between the thumb and index finger of the subject and released at a random time during a countdown. The subject catches the apparatus and the distance fallen is converted to reaction. Following two practice trials, subjects perform eight trials, and a mean distance value is used for analysis. This simple clinical measure has been evaluated by Eckner et al, and demonstrated utility in testing comparable to computerized testing methods²⁸. ⁴⁴

Grip Strength

Grip strength will be evaluated using a hydraulic hand dynamometer (Baseline Hydraulic Hand Dynamometer). The greatest force generated during three trials will be used for analysis²⁹.⁴⁵

Brain Pattern Analysis

The proprietors of HIRREM have repeatedly observed that EEG asymmetries in the temporal lobes (specifically at T3 and T4 in the 10-20 International System for EEG correspond to autonomic dysfunction. When T4 signals are dominant to T3 signals a sympathetic state is favored which is manifested as symptoms of anxiety, cardiovascular over-drive, and hyperarousal. When T3 signals are excessively dominant to T4 signals a parasympathetic state is favored which is manifested as symptoms of emotional numbness, cardiovascular underactivity, GI dysfunction, and under-arousal. Lateralization of autonomic activity is not a novel finding, it is in accord with a number of previously published studies which support a hypothesis of autonomic lateralization⁴⁶.

EEG balance at T3 and T4 suggests autonomic balance and benefit, and our preliminary results suggest that utilization of HIRREM at T3 and T4 has demonstrated success in ameliorating symptoms associated with autonomic disruption^{31,47} Preliminary data also demonstrate correlation between a T3/T4 temporal asymmetry score and objective physiological changes reflective of autonomic signaling to the heart at the baseline assessment (AAN T3/T4 2013

poster). Reduction in the sum of high frequency amplitudes at T3/T4 (reduced hyperarousal), has also been observed in subjects with hot flashes⁴⁸. Comparison of such activity at T3 and T4 over time will provide objective physiological outcome data regarding the effect of HIRREM on autonomic balance and function.

5) Statistical Analysis

Data will be analyzed using the most recent versions of SAS (SAS Institute, Inc., Cary, NC) or the R Statistical Computing Environment. Histograms and descriptive statistics will be examined to evaluate the distribution of study outcomes. Because this proposal is designed to estimate effect sizes for future randomized trials, analyses will primarily consist of providing point estimates of effect size for each outcome along with corresponding 95% Cls. Given that outcomes will be collected at multiple follow-up time points (V2, V3, and V4), effect estimates will be based on generalized linear models, which can accommodate within-subject correlations due to repeated assessment over time. Critically, estimates produced from this pilot study will need to be used cautiously for planning future research, as it is well known that estimates from small sample sizes tend to be upwardly biased (overestimated effect sizes, underestimated variability⁵³.

6) Participant Compensation

Participants in this research project will not receive any monetary compensation.

Human Subjects Protection:

1) Consent and Assent

Written informed consent, or assent and parental permission will be obtained by the research staff from each competent subject.

2) Confidentiality and Privacy

Confidentiality will be protected by collecting only information needed to assess study outcomes, minimizing to the fullest extent possible the collection of any information that could directly identify subjects, and maintaining all study information in a secure manner. To help ensure subject privacy and confidentiality, only a unique study identifier will appear on the data collection form. Any collected patient identifying information corresponding to the unique study identifier will be maintained on a separate master log. The master log will be kept secure, with access limited to designated study personnel. Following data collection subject identifying information will be destroyed at the earliest opportunity, consistent with data validation and study design, producing an anonymous analytical data set. Data access will be limited to study staff. Data and records will be kept locked and secured, with any computer data password protected. No reference to any individual participant will appear in reports, presentations, or publications that may arise from the study.

Brain State Technologies, LLC (BST) will assist with brain pattern analysis. To accomplish this, BST will be provided with the first 8 characters from the randomly generated, 36 character identifier that the HIRREM software generates for each participant's brain frequency and amplitude data, along with the participant's age and gender, which are believed important for understanding brain patterns. No other participant-specific information is provided.

3) Data and Safety Monitoring

The principal investigator will be responsible for the overall monitoring of the data and safety of study participants. The principal investigator will be assisted by other members of the study staff. Results will also be regularly reviewed with representatives of OSD, the funding agency.

Any collected patient identifying information corresponding to the unique study identifier will be maintained on a separate master log. The master log will be kept secure, with access limited to designated study personnel. Following data collection subject identifying information will be destroyed at the earliest opportunity, consistent with data validation and study design, producing an anonymous analytical data set. Data access will be limited to study staff. Data and records will be kept locked and secured, with any computer data password protected. No reference to any individual participant will appear in reports, presentations, or publications that may arise from the study.

A Medical Monitor, with knowledge of MRI, as well as HIRREM, will be identified. The Medical Monitor will review progress of the study, and any safety issues, with the PI on a monthly basis.

4) Reporting of Unanticipated Problems, Adverse Events or Deviations

Any unanticipated problems, serious and unexpected adverse events, deviations or protocol changes will be promptly reported by the principal investigator or designated member of the research team to the IRB and sponsor or appropriate government agency if appropriate.

Addendum (10.05.17):

This addendum briefly outlines the history, and the current status of this protocol and project to provide context for the revised protocol outlined above. Based on funding provided by a contract with US SOCOM, the initial 15 participants had all symptom, functional, physiological, imaging, biomarker outcomes. A subset also had evaluation of epigenetic markers. Following completion of the contracted work, the project was continued using other internal funding so that at total of 18 participants had all outcomes except for the biomarkers, and epigenetics. Thereafter, in order to expand the pilot data set, and to add participants from other branches of the military and Special Operations community, the study was continued with goal of enrolling up to 40 participants. However, due to lack of outside funding, all participants beyond number 18 did not receive MRI, biomarker, or epigenetic outcomes.

The protocol has now been modified to reflect the current study procedures and outcomes, removing mention of those prior outcome elements described above.

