Methods: This will be an open label, single-site, clinical research study. Up to 40 active duty military personnel, or recent Veterans, age 18 or older, who have been diagnosed with PTSD, have been treated for, are referred by military medical personnel for, or have active symptoms of military-related traumatic stress, with or without mild TBI, will be recruited to receive up to 24 HIRREM sessions over 2 weeks. The primary outcome will be differential change in the PCL-M from baseline to completion of HIRREM sessions. Secondary measures include differential change in the Insomnia Severity Index (ISI), the Center for Epidemiological Studies Depression Scale (CES-D), an anxiety measure (GAD-7), a quality of life measure (EQ-5D), an autonomic symptom measure (Compass 31), and a daily sleep diary, along with physiological measures including heart rate (HR), and blood pressure (BP), with calculation of heart rate variability measures (HRV), baroreflex sensitivity (BRS). Functional measures will include reaction time (drop-stick task), and grip strength (hydraulic dynamometer). If there is a history of TBI, a Rivermead Post-Concussion Symptoms Questionnaire (RPQ) will be added. There will be pre- and postintervention data collection for all measures (baseline, V1, and at completion of HIRREM sessions, V2). Self-report measures will be repeated by phone at 1, 3, and 6 months after completion of sessions (V3, V4, and V5 respectively). The sleep diary will be maintained from V1 until V3. A brainwave assessment will be obtained at V1.

Sample Size and Statistical Analysis: The primary statistical intent of this pilot clinical research study is to generate estimates of effect size in order to plan subsequent randomized studies. Given that outcomes will be collected at multiple follow-up time points (V2, V3, V4, and V5), effect estimates will be based on generalized linear models (GLM), which can accommodate within-subject correlations due to repeated assessment over time. While no directly relevant, controlled study data is currently available, a recent, national study of prolonged exposure therapy in veterans with PTSD (N=1,888) indicated a mean decrease on the PCL-M of 15.2 points (standard deviation = 20.0). Assuming a similar level of variability

in our population and a sample of 10 subjects, we expect to generate a 95% confidence interval for the mean change on the PCL-M with a half-width (1.96 x standard error) of \pm 12.4 points.

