This will be an open label, single site, pilot, clinical research study. Up to 40 active duty military personnel, or recent Veterans, age 18 or older, who have been diagnosed with PTSD, have received treatment for, are referred by military medical personnel for, or have active symptoms of militaryrelated traumatic stress, with or without mild TBI, will be recruited to receive up to 24 HIRREM sessions over 2 weeks. For those who self-refer, and do not have a prior diagnosis or treatment for PTSD, active symptoms will be identified by a screening PCL-M score of 50 or greater. Recruitment of 40 participants will allow us to achieve the goal of 36 participants to complete the intervention, allowing for the possibility of dropouts. The primary outcome will be differential change in the PCL-M from baseline to completion of HIRREM sessions. Secondary measures include the Insomnia Severity Index (ISI), the Center for Epidemiological Studies Depression Scale (CES-D), an anxiety measure (GAD-7), a quality of life measure (EQ-5D), an autonomic symptom measure (Compass 31), and a daily sleep diary, as well as physiological measures including heart rate (HR), and blood pressure (BP), with calculation of heart rate variability measures (HRV), and baroreflex sensitivity (BRS). Functional measures will include reaction time (drop-stick paradigm), and grip strength (hydraulic dynamometer), and analysis of brain patterns. If there is a history of TBI, a Rivermead Post-Concussion Symptoms Questionnaire (RPQ) will be added. There will be pre- and post-intervention data collection for all measures (baseline, V1, and at completion of HIRREM sessions, V2). Self-report measures will also be repeated by phone at 1, 3, and 6 months after completion of sessions (V3, V4, and V5 respectively). The online sleep diary will be maintained from V1 until V3. A brainwave assessment will be obtained at V1.

Participants/Subjects

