- Lack of internet or smart phone access (will maintain remote access daily sleep diary through 1 month post-HIRREM visit)

Participants are encouraged to discuss their participation with their health care provider following completion of the study because HIRREM may alleviate some of the need for medications they were on previously. Participants are requested to abstain from using any alcohol or recreational drugs during the intervention, and until the one month follow-up phone data collection since use of these substances may cause reversal or cessation of the benefits of HIRREM. In addition, the participants are also advised to suspend chiropractic, cranial-sacral therapy, and bio-energy work during the intervention, until the one month follow-up phone data collections and requests may be given to the patient and will be contingent upon the condition(s) being treated and will be at the discretion of the investigator.

1) Number of Subjects

The primary statistical intent of this pilot clinical research study is to generate estimates of effect size in order to plan subsequent randomized studies. While no directly relevant, controlled study data is currently available, a recent, national study of prolonged exposure therapy in veterans with PTSD (N = 1,888) indicated a mean decrease on the PCL-M of 15.2 points (standard deviation=20.0)³³. Assuming a similar level of variability in our population, we expect to generate a 95% confidence interval for the mean change on the PCL-M with a half-width (1.96 x standard error) of ± 12.4 points.

2) Number of HIRREM Sessions and Length of Study

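### The printed ±12.4 half-width for mean PCL-M change uses 1.96 where an estimated SD calls for a t quantile (±14.3 at n = 10); at the 36 planned completers the figure is ±6.8, so the outdated n matters more

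*Combined protocol and SAP*

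**What the plan says.** The combined protocol and SAP gives its expected precision twice.

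- **Synopsis, Sample Size and Statistical Analysis.** The planning SD comes from an external study of prolonged exposure therapy in veterans, which "indicated a mean decrease on the PCL-M of 15.2 points (standard deviation = 20.0"). Assuming similar variability "in our population and a sample of 10 subjects", the plan states "we expect to generate a 95% confidence interval for the mean change on the PCL-M with a half-width (1.96 x standard error) of" ±12.4 points.
- **Number of Subjects.** The same SD and the same ±12.4 appear, again defined with 1.96, but with no sample size: "Assuming a similar level of variability in our population, we expect to generate a 95% confidence interval for the mean change on the PCL-M".

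Two other places bear on the point.

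- **Research Design and Method, Overview.** The planned size is larger: "Recruitment of 40 participants will allow us to achieve the goal of 36 participants to complete the intervention".
- **Statistical Analysis.** The trial is one of estimation: "analyses will primarily consist of providing point estimates of effect size for each outcome along with corresponding 95"% intervals, and "effect estimates will be based on generalized linear models". No multiplier, variance estimator or degrees-of-freedom method is named there.

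**The concern.** The 20.0 is borrowed from another study and serves only for planning. The interval that the trial will produce has to use a standard error computed from its own participants. When the SD is estimated, the 95% multiplier is the t quantile on n − 1 degrees of freedom, which at n = 10 is clearly larger than 1.96. An interval built with 1.96 then covers the true mean less often than its label says.

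The trial's stated purpose is to supply effect estimates with intervals for planning randomized studies, and this half-width is the only precision figure that the documents give. It should be defined correctly and refer to the sample that the trial intends to have.

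**Working it through.** **Inputs**

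- SD of PCL-M change: 20.0 (synopsis and Number of Subjects; external planning value)
- n in the precision statement: 10 (synopsis only)
- Multiplier: 1.96, from "half-width (1.96 x standard error")
- Planned size: 40 recruited, 36 completers (Overview)

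**Step 1. Reproduce the printed figure.**

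SE = 20 / √10 = 6.325. Half-width = 1.96 × 6.325 = 12.40, which matches ±12.4.

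Number of Subjects gives no n, but solving back gives n = (1.96 × 20 / 12.4)² = (39.2 / 12.4)² ≈ 10.0. The figure there is therefore also the 10-subject figure.

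**Step 2. Use the multiplier for an estimated SD, n = 10.**

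t(0.975, 9 df) = 2.262. Half-width = 2.262 × 6.325 = 14.31, that is ±14.3. Ratio: 14.31 / 12.40 = 1.154, about 15% wider.

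This takes the sample SD to equal 20. Averaged over the sampling variation of the SD in normal data, the expected t half-width is ±13.9.

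**Step 3. Coverage of mean ± 1.96 × estimated SE, n = 10.**

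P(|t with 9 df| < 1.96) = 0.918. A simulation of 1,000,000 normal samples of 10 gave 0.919.

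**Step 4. Repeat at the planned size.**

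| n | SE | 1.96 × SE | t quantile | t × SE | Coverage of the 1.96 interval |
|---|---|---|---|---|---|
| 10 | 6.325 | 12.40 | 2.262 | 14.31 | 91.8% |
| 36 | 3.333 | 6.53 | 2.030 | 6.77 | 94.2% |
| 40 | 3.162 | 6.20 | 2.023 | 6.40 | 94.3% |

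At 36 completers the choice of multiplier moves the half-width by 6.77 − 6.53 = 0.24 points, on a scale that runs from 17 to 85.

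**Step 5. Separate the two effects.**

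With the multiplier held at 1.96, moving n from 10 to 36 takes the half-width from 12.40 to 6.53. With n held at 36, moving from 1.96 to t takes it from 6.53 to 6.77. The printed 12.4 is 12.4 / 6.77 = 1.83 times the t-based value for the planned completers.

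**The case against.** The strongest reply is that nothing has been miscalculated. The multiplier is printed next to the result, the sentence is conditional on similar variability, and if the SD were known to be 20, ±12.4 would be an exact 95% half-width. That stands: this is a disclosed planning approximation. It does not remove the point, because the sentence describes an interval that the trial will generate, and the SD will then be estimated.

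A second reply is that the effect is negligible at the size now planned. That also stands, and it sets the weight of the point.

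A reader might be tempted by three stronger readings, which the documents do not support.

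- **That the plan overstates its precision.** This holds only for a 10-subject study. The Overview plans 36 completers, and the addendum dated 10.05.17 reports that 18 participants already had outcome data. Against that design, ±12.4 understates the precision.
- **That the trial's reported intervals will fall short of 95% coverage.** The 1.96 appears only in the two sample-size statements. The Statistical Analysis section names no multiplier or degrees-of-freedom method, so this is a missing detail and not a stated error.
- **That outcomes in small subsets, such as the RPQ in those with a TBI history, are seriously affected.** The documents give no count of participants with TBI, so any subset size would be a guess.

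The Statistical Analysis section also warns that small samples tend to understate variability. That caution is apt, but it does not replace the t quantile.

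**Conclusion.** The point holds, with minor severity. For the 10-subject scenario in the synopsis, the 95% half-width with an estimated SD is ±14.3, not ±12.4, and the interval as defined covers about 92%. For the 36 completers now planned, it is ±6.8 with t against ±6.5 with 1.96, and coverage with 1.96 is 94.2%. The larger fault in the printed figure is its n.

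These results assume approximately normal changes, an SD near the planning value of 20.0, and a simple one-sample interval for the mean change. A repeated-measures model could give a somewhat different width. No test, stopping rule or decision threshold in the documents depends on the half-width, so the consequence is confined to how the expected precision is described.

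**What to change.** In the synopsis (Sample Size and Statistical Analysis) and in Number of Subjects:

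1. Define the half-width as the t quantile on n − 1 degrees of freedom times the standard error.
2. State the n in both places.
3. Print the value for the planned completers: ±6.8 for 36, at SD 20.0. If the 10-subject scenario is kept, label it as such and print ±14.3.

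Changing 12.4 to 14.3 alone would leave the outdated n in place and move the figure further from the planned design. The multiplier and the n should be corrected together.

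Optionally, add a sentence to Statistical Analysis saying that the model-based 95% intervals use t-based, small-sample degrees of freedom, for example Kenward-Roger, or a bias-corrected sandwich variance with t degrees of freedom.

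The cost is one sentence in each place and, for the optional part, a model setting in SAS or R. No change to the design, data collection or sample size is needed.

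### The ±12.4-point half-width for mean PCL-M change is the figure for 10 subjects; at the planned 36 completers the plan's own formula gives about ±6.5, and the Number of Subjects section gives no n at all.

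*Combined protocol and SAP*

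**What the plan says.** The synopsis (Sample Size and Statistical Analysis) and section 1) Number of Subjects both state that the aim is to estimate effect size for planning later randomized trials. Both take variability from a national study of prolonged exposure therapy, which "indicated a mean decrease on the PCL-M of 15.2 points (standard deviation=20.0" points).

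The synopsis then names the sample size behind its precision figure: "in our population and a sample of 10 subjects, we expect to generate a 95% confidence interval", with a half-width of 12.4 points. Section 1) uses the same SD but leaves the sample size out: "Assuming a similar level of variability in our population, we expect to generate a 95% confidence interval for the mean change on the PCL-M". The result it reports is nevertheless unchanged, an interval once more "with a half-width (1.96 x standard error) of ± 12.4 points".

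The planned size is given elsewhere. The synopsis allows up to 40 participants. The Overview under Research Design and Method says "Recruitment of 40 participants will allow us to achieve the goal of 36 participants to complete the intervention". The Addendum (10.05.17) agrees on the ceiling, saying that "the study was continued with goal of enrolling up to 40 participants". It also reports that "the initial 15 participants had all symptom, functional, physiological, imaging, biomarker outcomes" and that 18 had been studied before the expansion towards 40.

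**The concern.** In a study designed to estimate and not to test, the expected width of the confidence interval is the sample-size justification. This plan has one such figure, and it belongs to a sample of 10. That is neither the target (36 completers) nor the number already studied when this text was written (15, then 18).

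The problem is sharpest in section 1). That is where a reader looks for the size of the trial and what it will deliver, and without an n the ±12.4 can only be taken as the precision of this trial.

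Two things are at stake. A reader deciding whether 40 participants are warranted is given a width nearly double what that enrolment should produce. And the plan never says what precision its chosen size buys: the Overview explains 40 versus 36 by dropouts, and the Addendum explains the expansion by a wish for a larger pilot data set, but neither links the number to an interval width.

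**Working it through.** **Inputs, all from the plan**
- SD of PCL-M change: 20.0 (synopsis and section 1)).
- Multiplier: 1.96 × standard error (synopsis and section 1)).
- Reference mean change: 15.2 points (synopsis and section 1)).
- n = 10 (synopsis); 36 completers (Overview); up to 40 recruited (synopsis, Overview, Addendum); 15 and 18 already studied (Addendum).

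**Formula.** Half-width = 1.96 × SD/√n = 39.2/√n.

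**Reproducing the stated figure.** At n = 10, 39.2/3.162 = 12.40, which matches. Solving for n gives (39.2/12.4)² = 9.99, so 10 is the only whole number that fits.

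**The same formula at the sizes the plan mentions**

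| n | Source | Half-width (points) |
|---|---|---|
| 10 | Synopsis precision sentence | 12.40 |
| 15 | Addendum, initial participants | 10.12 |
| 18 | Addendum, before expansion | 9.24 |
| 36 | Overview, goal for completers | 6.53 |
| 40 | Recruitment ceiling | 6.20 |

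**Size of the mismatch at 36 completers**
- Ratio: 12.40/6.53 = √(36/10) = 1.90. Put the other way, the interval at 36 is about 47% narrower (1 − 6.53/12.40).
- In SD units: 12.40/20 = 0.62 as stated, against 6.53/20 = 0.33.
- Around the reference change: 15.2 ± 12.40 is 2.8 to 27.6, and 15.2 ± 6.53 is 8.7 to 21.7.

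**Could another reading give ±12.4 at the planned size?**
- Larger SD: at n = 36 it would need an SD of 12.4 × 6/1.96 = 38.0, nearly double the plan's 20.0.
- t quantile in place of 1.96: ±14.31 at n = 10, ±6.77 at n = 36 and ±6.40 at n = 40. None of these is 12.4.

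So under the plan's inputs the figure belongs to n = 10 and to no size the trial is now planned to have.

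**The case against.** The best defence is that nothing was miscalculated. The synopsis makes a conditional statement, names its n, and is correct. A reader of the whole document can carry that n over to section 1), where the SD and the reference study are the same. The discrepancy is also conservative, and section 5) Statistical Analysis sets no test or success threshold. Later trials would be planned from the observed estimates and intervals, not from this advance figure. On that view it is a minor matter of clarity.

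Much of this is fair. The arithmetic in the synopsis is sound, the trial is not too small because of this figure, and nothing downstream uses it. The documents also do not say where the 10 came from, so calling it a leftover from a smaller design would be inference.

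Two further cautions stand. Thirty-six is a goal under a ceiling of 40, not a fixed analysis n. And the planned estimates come from repeated-measures models, so the one-sample formula only approximates the width the trial will report.

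None of this removes the mismatch. The synopsis itself plans up to 40 participants and then describes precision for 10 without saying why. Section 1) drops the condition that made the statement true.

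**Conclusion.** The concern holds. The plan's only precision statement describes a sample of 10, while the design aims for 36 completers from up to 40 recruited. For that design the stated half-width is 1.9 times too wide: ±12.4 against ±6.5 at 36, or ±6.2 at 40.

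These values rest on the plan's own SD of 20.0 and multiplier of 1.96, and on reading completers as the n for the primary outcome. That reading is natural because the primary outcome is change from baseline to the end of sessions. If fewer than 36 complete, the half-width will lie between the two figures; at 18, for example, it is ±9.2.

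This should be fixed because it misstates a property of the design in a study whose purpose is estimation. It does not threaten the validity of any analysis, and it does not suggest a change in enrolment.

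**What to change.** Change the precision sentence in both places, the synopsis (Sample Size and Statistical Analysis) and section 1) Number of Subjects. Keep the SD of 20.0 and the 1.96 multiplier, state that the calculation is for 36 completers, and give the expected half-width for mean PCL-M change as ±6.5 points. In the synopsis this replaces the reference to 10 subjects; in section 1) it supplies the missing n.

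Two optional additions: the value at full recruitment (±6.2 at 40), and a note that the t quantile with 35 degrees of freedom gives about ±6.8 at 36 (2.030 × 20.0/6 = 6.77).

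If 10 was meant only as an illustration, say so in both places and still give the figure for 36.

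The cost is one sentence in each of two sections, with no added participants, procedures or analyses.
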